11.4.4 Supportive analyses

In case more than 2 discontinuations occur in this study, additional methods may be used to assess sensitivity of the results to different imputation techniques to deal with the missing data.

11.5 Analysis of secondary and exploratory variables

Corporate Confidential Information

11.5.2 Safety

Vital signs

All vital signs data will be listed by patient, visit and if ranges are available, abnormalities (and relevant orthostatic changes) will be flagged. Summary statistics will be provided by visit.

ECG evaluations

All ECG data will be listed by patient and visit/time, and abnormalities will be flagged. Summary statistics will be provided by visit/time.

Clinical laboratory evaluations

All laboratory data will be listed by patient and visit, and if normal ranges are available, abnormalities will be flagged. Summary statistics will be provided by visit.

Adverse events

All information obtained on adverse events will be displayed by patient.

The number and percentage of patients with adverse events will be tabulated by body system and preferred term. A patient with multiple adverse events within a body system is only counted once towards the total of this body system.

Corporate Confidential Information

11.5.3 Pharmacokinetics

Corporate Confidential Information

11.5.4 Pharmacokinetic / pharmacodynamic interactions

Not Applicable.

11.5.5 Other assessments

Corporate Confidential Information

11.6 Sample size calculation

The proposed sample size for this study is 12 patients (to complete the study). Assuming CFZ533 is associated with 38% normalization of the TSH levels after 12 weeks of treatment (which is consistent with the response rate seen with Rituximab in 26 weeks in one small, open-label study ([Heemstra et al 2008](#)), there is around 89% power to detect a proportion of TSH responders significantly higher than 5% (this would be achieved with at least 3/12 responders), with a type I error of 10%. Additionally, this sample size provides 98% power to detect normalization of the total T3 (and free T4, respectively) below the upper limit of the normal range (2.79 nmol/L and 22.7 pmol/L, respectively). The assumed baseline levels are 7.2 nmol/L for total T3 and 58.55 pmol/L for free T4, which are the average values reported in GD patients in [Andrade et al \(2001\)](#). The assumed standard deviation for the change from baseline are 4.24 nmol/L and 34.58 pmol/L respectively.

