Investigational and reference therapy	
 Patients will receive CFZ533 10mg/kg IV infusion on Study Days 1, 15, 29, 57, and 85.

Efficacy/PD assessments	
• TSH• Free T4• Total T3
Safety assessments	
• Physical examinations• ECG• Vital signs (BP, HR, pulse, temperature)• Hematology• Blood chemistry• Urinalysis• Pregnancy test• Blood coagulation panel• Monitoring for AEs/SAEs
	Corporate Confidential Information
Data analysis	
One of the primary aims of this study is to assess the effects of CFZ533 on thyroid function, focusing on TSH, free T4 and total T3 levels, in Graves' disease after 12 weeks of treatment. The effects of CFZ533 on thyroid function will be primarily assessed by the proportion of patients whose TSH levels normalize (>0.35 mU/L) after 12 weeks of treatment. Another important aim of this study is to assess the effects of CFZ533 on free T4 and total T3 after 12 weeks of treatment.
 
One of the main efficacy criteria is to show that the proportion of patients with normalization of TSH (above 0.35 mU/L) after 12 weeks of treatment with CFZ533 is statistically greater than 5%, according to a 1-sided exact test for proportions with a 10% type I error. This will be achieved if we observe at least 3/12 responders since in that case the lower bound of an 80% confidence interval for the proportion of responders will be about 10%. The other two main efficacy criteria are to show that the average free T4 and total T3 levels are significantly reduced after 12 weeks of treatment, according to a 1-sided paired t-test with a 10% type I error.

Key words	
• Graves' disease (GD), hyperthyroidism• CFZ533• CD40, CD154• TSH• T3, T4•

1 Introduction

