11.4.1 Variable(s)

The effects of CFZ533 on thyroid function will be primarily assessed by the proportion of patients whose TSH levels normalize (above 0.35 mU/L) after 12 weeks of treatment. They will also be assessed by the difference in mean total T3 and free T4 between baseline and after 12 weeks of treatment.

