11.4.2 Statistical model, hypothesis, and method of analysis

One of the main efficacy criteria for this study is to show that the proportion of patients with normalization of TSH (above 0.35 mU/L) after 12 weeks of treatment with CFZ533 is statistically greater than 5%, according to a 1-sided exact test for proportions with a 10% type I error. This will be achieved if we observe at least 3/12 responders since in that case the lower bound of an 80% confidence interval for the proportion of responders will be about 10%. The other efficacy criteria are that there is a significant reduction in average total T3 and free T4 after 12 weeks of treatment, according to a 1-sided paired t-test with 10% type I error for each of these two endpoints.

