6.1.1 Variables

The effects of CFZ533 on thyroid function will be primarily assessed by the proportion of

patients whose TSH levels normalize (above 0.35 mU/L) after 12 weeks of treatment (TSH responders). They will also be assessed by the difference in mean total T3 and free T4 between baseline (Day 1, predose) and after 12 weeks of treatment, and the proportion of patients whose total T3 or free T4 levels normalize (below ULN) after 12 weeks of treatment.

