6.1.2 Descriptive analyses

TSH levels will be summarized over time together with their changes from baseline. The frequency of TSH responders will be summarized for each timepoint. Same statistical analysis will be performed for the frequency of patients whose total T3 and free T4 levels normalize. Results will also be presented for free T3 and total T4.

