6.1.3.2 Supportive analyses

In case more than 2 discontinuations occur in this study, additional methods may be used to assess sensitivity of the results to different imputation techniques to deal with the missing data.

Total and free T3 and T4 will be analyzed using a repeated measures model with baseline as a covariate and visit as the repeated effect. The difference from Day 1 at each timepoint will be presented along with the 80% CI and the 2 sided p-value.

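### Does the 98% power for total T3 and free T4 in protocol Section 11.6 promise more than the planned test can show?

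*Protocol*

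**What the plan says.** Protocol Section 11.6 sets 12 completers and, after the TSH calculation, adds: "this sample size provides 98% power to detect normalization of the total T3 (and free T4, respectively) below the upper limit". The limits are 2.79 nmol/L for total T3 and 22.7 pmol/L for free T4. The assumed baselines are 7.2 nmol/L and 58.55 pmol/L. On variability it says: "The assumed standard deviation for the change from baseline are 4.24 nmol/L and 34.58 pmol/L respectively".

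The analysis sections describe a comparison of means. Protocol Section 11.4.1 names "the difference in mean total T3 and free T4 between baseline and after 12 weeks of treatment" as the variable. The criterion in Section 11.4.2 reads: "there is a significant reduction in average total T3 and free T4 after 12 weeks of treatment, according to a 1-sided paired t-test". Each hormone is tested at a type I error of 10%. The synopsis (Data analysis) and SAP Section 6.1.3 set the same test.

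Normalisation of the two hormones is a separate quantity that appears in the SAP. Section 6.1.1 lists "the proportion of patients whose total T3 or free T4 levels normalize (below ULN) after 12 weeks of treatment", and Section 6.1.2 places it among the descriptive summaries: "Same statistical analysis will be performed for the frequency of patients whose total T3 and free T4 levels normalize". Section 6.1.3.3 plots these frequencies. The visible text attaches no null rate, threshold or test to them.

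**The concern.** Taken literally, Section 11.6 claims near-certain success in demonstrating something that no visible test examines. The preceding sentence of that section uses normalisation for a response in the individual patient (TSH), so a reader may carry that meaning over to total T3 and free T4.

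The two readings are far apart. A fall in the mean can be statistically significant while the mean is still well above the upper limit. If a significant t-test were later presented as reaching a normalisation goal with 98% power, the evidence on two primary endpoints would be overstated, in a study meant to inform whether development continues.

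**Working it through.** **Inputs.** All are from protocol Section 11.6, except the test and its level, which are from Section 11.4.2: n = 12, one-sided type I error 0.10, paired t-test of zero mean change.

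| | Total T3 (nmol/L) | Free T4 (pmol/L) |
|---|---|---|
| Assumed baseline | 7.2 | 58.55 |
| Upper limit of normal | 2.79 | 22.7 |
| SD of change | 4.24 | 34.58 |

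**Step 1: reproduce the stated figure.** Suppose the true mean falls from baseline to the upper limit.

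- Fall: 7.2 − 2.79 = 4.41; 58.55 − 22.7 = 35.85.
- Standardised fall: 4.41/4.24 = 1.040; 35.85/34.58 = 1.037.
- Power = P(T > 1.3634), where T is noncentral t with 11 degrees of freedom and noncentrality equal to the standardised fall × √12.
- Result: 0.9853 for total T3 and 0.9849 for free T4, which agrees with the stated 98%.

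Other choices fit less well. A normal approximation gives 99.0% for each hormone, and a two-sided 10% t-test gives 95.8% and 95.7%. So the match supports the planned one-sided t-test, with the upper limit used only to fix the size of the assumed fall.

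**Step 2: check the one rival explanation.** A rule of at least 3 of 12 patients normalising, with a true rate of 50%, has probability 98.1%, also close to 98%. Neither document states such a rule or rate for these hormones, and the calculation would not use the baselines or SDs that Section 11.6 supplies. It is probably a coincidence.

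**Step 3: see what the literal reading would give.** If the true mean lies exactly on the limit, a one-sided 10% test that the mean is below the limit has noncentrality 0. Its power is then 10% whatever the SD. The observed mean would fall below the limit with probability 50% (symmetric sampling distribution).

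**Step 4: find the smallest significant fall** at the planning SD, 1.3634 × SD/√12.

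- Total T3: 1.67, leaving 7.2 − 1.67 = 5.53, and 5.53/2.79 = 1.98 times the limit.
- Free T4: 13.6, leaving 58.55 − 13.6 = 44.9, and 44.9/22.7 = 1.98 times the limit.

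Steps 3 and 4 confirm that a significant t-test does not show normalisation. They do not show an error in the 98%, because the planned test does not aim at normalisation.

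**Step 5: see whether the outputs would hide persisting high levels.** They would not. Besides the normalisation frequencies and plots, SAP Section 6.1.3.2 provides repeated-measures estimates: "The difference from Day 1 at each timepoint will be presented along with the 80% CI and the 2 sided p-value". A significant fall to twice the limit would appear as a low proportion normalised and as mean levels plainly above the limit.

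**The case for a change.** The best argument for rewording is that the sentence makes normalisation the thing detected, whereas the TSH sentence before it separates the assumed rate (38%) from the hypothesis tested (a proportion above 5%). A power statement for primary endpoints should name its hypothesis. The gap is also not trivial: a true fall of half the assumed size, leaving each mean at 1.79 times the limit (4.995/2.79 and 40.625/22.7), would still be significant about 67% of the time.

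What stands is that the wording is imprecise and the alternative would be clearer. The rest carries less weight:

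- Power to detect an effect is common shorthand for the power of the planned test when that effect is true. Here the baseline, limit and SD stand beside the claim, so the meaning can be recovered.
- The 10% and 50% figures concern a test and an outcome that the visible text does not plan. They also hold only if the week-12 mean sits exactly on the limit, which the protocol does not state.
- Reaching significance well short of the assumed effect is a property of any test with such high power. It follows from choosing a mean reduction as the criterion, and the synopsis says so openly: "average free T4 and total T3 levels are significantly reduced after 12 weeks of treatment, according to a 1-sided paired t-test". Rewording Section 11.6 would not alter it.
- Protocol Section 13.1 requires a written, approved amendment for any protocol change, which is out of proportion to one explanatory sentence.

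**Conclusion.** No change to the plan follows. The 98% is correct for the test that will be run (98.5% recomputed for both hormones); the looseness lies in naming the assumed effect as the thing detected. The sample size, the tests, the success criteria and the SAP outputs would be the same under clearer wording, so an analyst following the plan as written reaches the same conclusions. The study report only needs to describe a significant t-test as a reduction in the mean, and to take any statement on normalisation from the planned proportions.

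This rests on the inference that the assumed week-12 mean equals the upper limit, on approximate normality of the changes, and on 12 patients contributing data. It also rests on the visible text: the interim-analysis sections (protocol Sections 3.5 and 11.8, SAP Section 3) and much of protocol Section 11.5 are redacted, so the absence of a normalisation test can be confirmed only for what is shown.

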11.7 Power for analysis of key secondary variables

Not applicable

11.8 Interim analyses

Corporate Confidential Information

Corporate Confidential Information

12 Ethical considerations

12.1 Regulatory and ethical compliance

This clinical study was designed and shall be implemented and reported in accordance with the ICH Harmonized Tripartite Guidelines for Good Clinical Practice, with applicable local regulations (including European Directive 2001/20/EC, US Code of Federal Regulations Title 21, and Japanese Ministry of Health, Labor, and Welfare), and with the ethical principles laid down in the Declaration of Helsinki.

12.2 Responsibilities of the investigator and IRB/IEC

Before initiating a trial, the investigator/institution should obtain approval/favorable opinion from the Institutional Review Board/Independent Ethics Committee (IRB/IEC) for the trial protocol, written informed consent form, consent form updates, patient recruitment procedures (e.g. advertisements) and any other written information to be provided to patients. Prior to study start, the investigator is required to sign a protocol signature page confirming his/her agreement to conduct the study in accordance with these documents and all of the instructions and procedures found in this protocol and to give access to all relevant data and records to Novartis monitors, auditors, Novartis Quality Assurance representatives, designated agents of Novartis, IRBs/IECs, and regulatory authorities as required. If an inspection of the clinical site is requested by a regulatory authority, the investigator must inform Novartis immediately that this request has been made.

For multi-center trials, a Coordinating Investigator will be selected by Novartis around the time of Last Patient Last Visit to be a reviewer and signatory for the clinical study report.

12.3 Publication of study protocol and results

Novartis assures that the key design elements of this protocol will be posted in a publicly accessible database such as clinicaltrials.gov. In addition, upon study completion and finalization of the study report the results of this trial will be either submitted for publication and/or posted in a publicly accessible database of clinical trial results.

13 Protocol adherence

This protocol defines the study objectives, the study procedures and the data to be collected on study participants. Additional assessments required to ensure safety of patients should be administered as deemed necessary on a case by case basis. Under no circumstances should an investigator collect additional data or conduct any additional procedures for any research related purpose involving any investigational drugs.

Investigators must apply due diligence to avoid protocol deviations. If the investigator feels a protocol deviation would improve the conduct of the study this must be considered a protocol amendment, and unless such an amendment is agreed upon by Novartis and approved by the IRB/IEC/REB it cannot be implemented. All significant protocol deviations will be recorded and reported in the CSR.

1.1 Scope of document

The RAP documents contain detailed information to aid the production of Statistics & Programming input into the Clinical Study Report (CSR) for trial “CCFZ533X2205”.

The Statistical analysis plan (SAP) describes the implementation of the statistical analysis planned in the protocol.

1.2 Study reference documentation

This SAP is based on protocol v01 (amended protocol) dated 16-Mar-2016.

1.3 Study objectives

1.3.1 Primary objective

To assess the effects of CFZ533 on thyroid function in Graves' disease (GD) after 12 week treatment.

1.3.2 Secondary Objective

To assess the safety and tolerability of CFZ533 (10 mg/kg IV for 12 weeks) up to 36 weeks.

1.3.3 Exploratory objectives

[figure not shown]
Corporate Confidential Information

1.4 Study design and treatment

This is a non-confirmatory, open-label, one treatment arm study in patients with newly diagnosed GD.

A total of approximately 15 patients will be enrolled and treated with CFZ533 to ensure approximately 12 completers. For each patient, the study will consist of a screening epoch of up to 28 days, a baseline evaluation, a 12-week treatment epoch, 24-week follow up epoch after the last dosing of CFZ533 on Study Day 85, and a study completion evaluation on Study Day 253. Patients who discontinue the drug before having completed 4 weeks of treatment and 4 week efficacy and safety evaluations will be replaced with a newly enrolled patient. The study design is presented in Figure 1-1.

Figure 1-1 Study design

2 First interpretable results (FIR)

First interpretable results (FIR) will be provided for this trial.

The study FIR template (mock slides) can be found in CREDI in the study RAP folder.

The template shows the analysis / results to be presented in the FIR. Study outputs required to be created at the time of the FIR will be highlighted in TFL shells document and marked as "Key" in the Programming Deliverables Tracker (PDT) output list.

3 Interim analyses

Corporate Confidential Information

4 Statistical methods: Analysis sets

For all analysis sets, patients will be analyzed according to the study treatment received.

All patients that received study drug and with no protocol deviations with relevant impact on safety will be included in the safety analysis set.

The PK analysis set will include all patients with at least one available valid (i.e. not flagged for exclusion) PK concentration measurement, who received any study drug and experienced no protocol deviations with relevant impact on PK data.

The PD analysis set will include all patients with any available PD data, who received any study drug and experienced no protocol deviations with relevant impact on PD data, who have completed at least 4 weeks of treatment with CFZ533.

The analysis sets and protocol deviation codes are related as follows:

Table 4-1 Protocol deviation codes and analysis sets

Category Deviation code	Text description of deviation	Data exclusion
Subjects are excluded from all (safety) analysis in case of these PDs:		
I01	Deviation from inclusion criteria 1 (ICF not obtained)	Yes
	No study drug taken	Yes
Subjects are excluded from PK analysis in case of these PDs:		
I01	Deviation from inclusion criteria 1 (ICF not obtained)	Yes
	No study drug taken	Yes
Subjects are excluded from PD analysis in case of these PDs:		
I01	Deviation from inclusion criteria 1 (ICF not obtained)	Yes
	No study drug taken	Yes

Category Deviation code	Text description of deviation	Data exclusion
	Subject took any prohibited medications interfering with efficacy	Yes
Subjects are excluded from PK and PD analysis in case of these PDs:		Exclude subject from PK and PD analysis sets
I01	Deviation from inclusion criteria 1 (ICF not obtained)	Yes
	No study drug taken	Yes

There are two categories of medications which are considered rescue medication. In order to identify these for programming purposes these are included in the protocol deviations dataset with codes of O01 and O02 (oral corticosteroids and anti-thyroid drugs) however they are not protocol deviations so will not be included in the protocol deviations listing, instead they will be included in a separate rescue medication listing.

In PD outputs the following rules will be applied to subjects who received rescue medication

- Data post rescue medication will be flagged in the listings with a * and a footnote added to explain.
- Figures showing individual profiles will appear as red lines from the point at which the rescue medication was taken and a footnote added to explain.
- In summary tables and summary figures datapoints after rescue medication will be excluded and a footnote added to explain.
- In the inferential analyses datapoints after rescue medication will be excluded and a footnote added to explain. For the longitudinal models the model is expected to provide unbiased results under the assumption that the rescue medication intake can be considered dependent only on previously observed values (MAR – missing at random).

If updates to this table are needed, an amendment to the SAP needs to be implemented prior to DBL.

5 Statistical methods for Pharmacokinetic (PK) parameters

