No comparator: No previous clinical experience with an anti-CD40 blocking agent in patients with GD exists. Given the nature of TSH as described above, the likelihood of observing a response to placebo is very low. Data provided in ([Heemstra et al 2008](#)) regarding the natural variability of TSH levels in this patient population in the absence of treatment were used to predict, via simulations, the proportion of patients treated with placebo that would be expected to rise above 0.3 mU/L within 12 weeks simply due to random variability. This proportion is predicted to be less than 1%. Corporate Confidential Information

Therefore, inclusion of a placebo arm is considered unnecessary.

Patient population: Graves' hyperthyroid patients Corporate Confidential Information

Withholding standard of care treatment: Withholding standard of care treatment for Graves' hyperthyroidism (ATD, radio-Iodine or surgery) for 12 weeks during the clinical study treatment period is justified for two reasons:

- 1) The presence of hyperthyroidism for 12 weeks is unlikely to result in permanent complications, especially when patients are adequately treated with beta blockers (e.g., if the heart rate is controlled)
- 2) A delay of 12 weeks is unlikely to impact the ultimate efficacy and safety of definitive treatment for Graves' hyperthyroidism. Patients will undergo rescue therapy with the standard of care for Graves' hyperthyroidism if they meet the stopping criteria.

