6.9 Rescue medication

Patients may receive standard of care treatment for Graves' hyperthyroidism at the discretion of the investigator in case of worsening of the disease. Patients will be discontinued from the study in this case as described in [Section 7.1](#). Rescue medication is to be provided by the study center or personal physician.

Use of rescue medication must be recorded on the Concomitant medications/Significant non-drug therapies CRF after start of study drug.

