7.1 Discontinuation of study treatment

Patients may voluntarily discontinue study treatment for any reason at any time.

The investigator **must** discontinue study treatment for a given patient if, on balance, he/she believes that continuation would be detrimental to the patient's well-being.

Study treatment **must** be discontinued under the following circumstances:

- Patient withdraws consent
- Pregnancy
- Grade 3 or higher allergic reaction
- Acute, Grade 3 or higher infection as judged by the Investigator

The study treatment should be discontinued if:

- Clinically significant worsening of Graves' disease, eg. beta-blocker unable to control the symptoms of hyperthyroidism, at the discretion of the Investigator.
- New onset atrial fibrillation or angina.
- On balance, the investigator believes that continuation would be detrimental to the patient's well-being.

Discontinuation of study treatment will be at the discretion of the Investigator, under the following circumstances:

- Use of prohibited treatment as per [Section 5.2](#).
- Any other protocol deviation that results in a significant risk to the patient's safety

Patients who discontinue study treatment or who decide they do not wish to participate in the study further should NOT be considered withdrawn from the study UNLESS they withdraw their consent (see [Section 7.3](#)). Where possible, they should return for the assessments defined in the [Assessment table](#). If they fail to return for these assessments for unknown reasons, every effort (e.g. telephone, e-mail, letter) should be made to contact them as specified in [Section 7.2.1](#). Patients who discontinue the drug before having completed 4 weeks of treatment and 4 week efficacy and safety evaluations will be replaced with a newly enrolled patient.

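### The SAP's rescue definition is narrower than the protocol's standard of care: no rule removes hormone values after thyroid surgery, and a radio-iodine patient appears to be deleted whole

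*SAP*

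**What the plan says.** **Rescue in the SAP.** Section 4 (Analysis sets) states: "There are two categories of medications which are considered rescue medication". It gives them codes O01 and O02 and names them as "oral corticosteroids and anti-thyroid drugs". It adds that they are not protocol deviations. Four rules follow for pharmacodynamic (PD) outputs: flag later values in listings, mark them in individual profiles, drop them from summaries, and drop them from inference. The last reads: "In the inferential analyses datapoints after rescue medication will be excluded and a footnote added to explain".

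**Rescue in the protocol.** Section 6.9 is wider: "Patients may receive standard of care treatment for Graves' hyperthyroidism at the discretion of the investigator in case of worsening of the disease". Section 3.2 shows what standard of care covers: "Withholding standard of care treatment for Graves' hyperthyroidism (ATD, radio-Iodine or surgery) for 12 weeks". The same section says that patients who meet the stopping criteria receive standard of care as rescue therapy.

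**After rescue.** Section 6.9 continues: "Patients will be discontinued from the study in this case as described in" section 7.1. Section 7.1, however, treats patients who stop study drug as still in the study unless they withdraw consent, and says: "Where possible, they should return for the assessments defined in the" assessment table.

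**Prohibited treatment.** Protocol Table 5-1 lists radioactive and cold iodine, methimazole and propylthiouracil, among others. Surgery is not listed. SAP Table 4-1 excludes from PD analysis any patient who took prohibited medication that interferes with efficacy.

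**The concern.** The SAP's principle is that hormone values after rescue should not be read as study-drug effect. It applies that principle to one of the three standard-of-care routes that the protocol names. The other two fall elsewhere, and differently.

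Thyroid surgery lowers T3 and T4 directly. A patient who worsens on CFZ533 and has a thyroidectomy would then supply falling hormone values that are summarised and modelled with the rest. The error favours the drug and comes from patients in whom it failed. For radio-iodine the problem is different: the patient seems to leave the PD set altogether, although SAP section 6.1.3.1 would count a discontinuation after week 4 as a non-response.

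With 12 completers and a success rule of three responders, one or two patients handled differently can matter.

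**Working it through.** **1. The plan's own figures (protocol section 11.6; rule in 11.4.2).** Inputs: n = 12, null 5%, alternative 38%, success at 3 or more responders, one-sided 10%.
- Exact binomial: P(X ≥ 3 | 12, 0.05) = 0.0196 and P(X ≥ 3 | 12, 0.38) = 0.893. The plan states about 89% power.
- Lower 80% Clopper-Pearson limit for 3/12: 0.096. The plan states about 10%.
- Paired t-test, noncentral t, SDs of change 4.24 nmol/L and 34.58 pmol/L: total T3 fall 7.2 − 2.79 = 4.41, power 0.985; free T4 fall 58.55 − 22.7 = 35.85, power 0.985. The plan states 98%.

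All reproduce. The design figures are not in dispute.

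**2. The three routes side by side.**

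| Route (protocol 3.2) | SAP rescue code | In Table 5-1 | Result under the SAP as written |
|---|---|---|---|
| Anti-thyroid drug | Yes | Yes | Later values removed, patient kept |
| Radio-iodine | No | Yes | Appears to remove the whole patient (Table 4-1) |
| Surgery | No | No | Nothing removed |

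**3. Where values after surgery can go.** TSH, T3 and T4 are scheduled to Day 253, and section 7.1 asks for return visits, so such values can exist. They can enter:
- the by-visit summaries and frequencies of normalisation (SAP 6.1.2);
- the repeated measures model for T3 and T4 (SAP 6.1.3.2);
- the week-20 results (SAP 6.1.3);
- the week-12 total T3 and free T4 tests, if surgery falls between about Day 57 and Day 85, or if a later value is taken as the last recorded one. SAP 6.1.3.1 sets an earliest time for that value (8 weeks of treatment) but no latest.

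**4. Size per patient for T3 and free T4.** Scenario: one of 12 falls from the assumed mean baseline to the upper limit of normal (ULN), with no earlier change.
- Shift in mean: 35.85 / 12 = 2.99 pmol/L; 4.41 / 12 = 0.37 nmol/L.
- Mean fall needed for significance, t(0.90, 11) × SD / √12: 1.363 × 34.58 / 3.464 = 13.6 pmol/L; 1.363 × 4.24 / 3.464 = 1.67 nmol/L.
- Ratio: 2.99 / 13.6 and 0.37 / 1.67, each about 22%.
- If all other patients have no mean change and the SD stays as stated, the approximate chance of a significant result is 10% with no such patient, 16% with one and 24% with two.
- In any by-visit frequency, one patient is 1/12 = 8.3 percentage points.

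**5. Deleting a treatment failure (radio-iodine).** With two TSH responders, P(X ≥ 2 | n, 0.05) = 1 − 0.95ⁿ − n × 0.05 × 0.95ⁿ⁻¹:
- n = 12: 1 − 0.540 − 0.341 = 0.118, above 10%.
- n = 11 (one failure deleted): 0.102, still above.
- n = 10 (two deleted): 1 − 0.599 − 0.315 = 0.086, below 10%.

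Two deletions would turn a failed criterion into a met one with no change in the number of responders.

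**The case against.** **Surgery as rescue is partly a reading.** Section 6.9 is headed rescue medication, and surgery enters only through the design rationale in 3.2. This is fair: no passage says that surgery was expected. But 3.2 itself links rescue therapy to standard of care, and exclusion criterion 4 admits patients who stopped anti-thyroid drugs for lack of efficacy or tolerability, so a non-drug route is plausible.

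**The PD set already bars deviations with relevant impact.** Table 4-1, which implements that clause, covers prohibited medications. Surgery is not in Table 5-1, so the clause does not clearly reach it.

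**A reader might infer that radio-iodine falls are also counted as CFZ533 effect.** The documents do not support this. Table 5-1 with Table 4-1 points to removal of the patient, provided that the use is coded to that row. Some doubt remains, because anti-thyroid drugs are in the same table and the SAP treats them as non-deviations.

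**A reader might infer that the primary TSH result is seriously exposed.** If one patient counted as a responder only because of surgery, the chance of reaching 3/12 under the 5% null would rise from 2.0% to 10.2%. But that patient would need surgery, then a TSH above 0.35 mU/L, recorded late enough to meet the exception in SAP 6.1.3.1. The default for discontinuation after week 4 is non-response, and standard of care is meant to be withheld for 12 weeks. The exposure is narrow.

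**The per-patient shift is an upper-end scenario.** This stands for the week-12 tests. With later data removed, the last-value rule would use the Day 57 value, so the distortion there is only the change after Day 57.

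**The data are visible.** Non-drug therapies are recorded on the CRF, concomitant therapies are listed, and profiles are plotted. In about 15 patients a thyroidectomy would be noticed. That makes the problem detectable, but it does not change what the pre-specified analysis does.

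**Conclusion.** The point holds for data handling. The SAP's closed list of two rescue categories omits two of the three standard-of-care routes in the protocol. Followed as written, it keeps hormone values after thyroid surgery. The main exposure is T3, T4 and the visits after week 12. The week-12 T3 and free T4 tests are exposed only in a narrow window or through the last-value rule, and the week-12 TSH responder analysis only slightly. Radio-iodine does not inflate the hormone effect, but it appears to remove a treatment failure from the denominator, in tension with the non-responder rule.

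The size is illustrative: about 3.0 pmol/L in mean free T4 and 0.37 nmol/L in mean total T3 per affected patient of 12. This assumes a fall from mean baseline that ends at the ULN and no change before surgery. The documents give no frequency of radio-iodine or surgical rescue, so no expected bias can be stated. The study is non-confirmatory, but its result decides whether development continues, so the rule should be settled before database lock.

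**What to change.** Amend SAP section 4 before database lock, as that section itself foresees:

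- For data handling, define rescue as any standard-of-care therapy for Graves' hyperthyroidism named in the protocol (anti-thyroid drugs, radio-iodine, thyroid surgery) started after first dose, plus the oral corticosteroid category already listed. Identify cases from the CRF page for concomitant medications and significant non-drug therapies.
- Apply the existing flagging and exclusion rules to all of these from the start date.
- Keep these patients in the PD set, subject to its 4-week requirement, so that the non-responder rule applies to them.
- State that a post-rescue value cannot make a patient a responder and cannot be carried forward.
- Leave cold iodine under the prohibited-treatment row. The protocol does not call it standard of care.
- Reconcile protocol section 6.9 (discontinued from the study) with section 7.1 (return for assessments), so that it is clear which post-rescue data are expected. No clinical rule is proposed here.

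Cost: one or two extra programming codes and no new data collection. Slightly more data are truncated, and the repeated measures model relies somewhat more on the SAP's missing-at-random assumption. Sample size and power are unchanged.
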